### 11.3 Planned Interim Analyses

The safety data will be analyzed periodically for review by the DSMB. Safety Review

#### 11.3.1 Efficacy Review

N/A

## 11.4 Final Analysis Plan (IR-1, RC-4)

Each primary outcome will be compared between the SDF and ART+FV groups. For tooth pain, a 95% confidence interval (CI) based on a t-test for the difference in mean responses (SDF minus ART+FV) will be computed. If this confidence interval lies within the interval  $(-\infty, 8)$  we may conclude 'non-inferiority' of SDF relative to ART+FV treatment. The confidence interval may secondarily be examined to assess possible superiority of one intervention over the other. For arrest rate, a 95% CI for the difference in rates (based on a z statistic) will be computed. If this confidence interval lies within the interval  $(-0.09, 1)$  we may conclude 'non-inferiority' of the SDF relative to ART+FV treatment. As above, possible superiority of one intervention over the other may also be assessed. For other outcomes, we will also compute 95% CI for differences in means (or proportions for binary outcomes). These secondary outcomes will be assessed in an exploratory manner for possibly superiority or inferiority based on appropriate margins.

We will seek to corroborate initial results using a generalized estimating equations (GEE) approach. For each outcome we will fit a GEE (marginal) model that includes a treatment indicator and prognostic variables (including sociodemographic variables, medical conditions, and oral health behaviors). Appropriate link functions (e.g., logit link for binary outcomes and identity link for continuous outcomes) will be specified and an exchangeable working correlation matrix used to allow for correlations within site. The arrest outcome will be analyzed as a binary outcome (as described in the sample size section), and secondarily as the number of arrested lesions assuming an appropriate distribution (e.g., negative binomial) and link function (e.g., log link). Robust t tests with correction for a small number of clusters will be used to test for treatment effects and corresponding 95% confidence intervals computed.

Secondarily, we will extend the above GEE approach to analyze the repeated (baseline, 26 and 52-week) measures for each outcome. The models for each outcome will include the same prognostic variables as before, as well as time and a time by treatment interaction. We will allow for correlations among the repeated measures, e.g., using a first-order autocorrelation structure. If a substantial within-facility correlation is found we may need to incorporate facility as a second cluster levels (within which person – the first cluster level – is nested). We will estimate and test (via a robust t-test) the interaction term to compare trends over time for the two interventions. If the use of two cluster levels is not found to be feasible in the GEE approach, we will consider a generalized mixed effects model approach.

**Causal Inference standards (CI-1, CI-2, CI-3, CI-4):** Our use of randomization and adjustment in regression models should be sufficient to provide causally interpretable intervention effect estimates; special causal inference techniques such as propensity score or instrumental variable methods often indicated for observational studies, will therefore not be necessary for our data analysis. We will avoid biases in causal inferences about the intended interventions by using an intent-to-treat approach, in which individuals are analyzed according to randomized groups without regard to (extent of) treatment actually received.

**Sensitivity Analyses IR-5:** We will check sensitivity of conclusions to model assumptions as well as methodological decisions such as outcome definition. In particular, for the arrest outcome, our primary analysis is based on a binary indicator of 'complete' arrest of all lesions for an individual. We will seek to corroborate results from this approach with an alternative approach analyzing

number of lesions arrested. For the GEE analyses, planned for all outcomes, sensitivity will be assessed in part by using alternative working covariance structures and alternative sets of predictors. For some outcomes, alternative distributions will be considered; for example, for number of arrested lesions, possible distributions include Poisson, negative binomial, zero-inflated Poisson (ZIP), and zero-inflated negative binomial (ZINB). Sensitivity to assumptions regarding missing data will also be investigated as described further below.

Missing Data. *(a) Methods to prevent and monitor missing data (MD-1, IR-7):* All questionnaires (using tablets) and dental assessment forms (using paper), will be managed in an electronic database (REDCap) by study staff. Weekly quality control checks will be run for outliers, entry errors, missing data, and potential data anomalies. Statistical analyses, summary and missing data reports will be generated by the study biostatistician ([name]) monthly during the study. *(b) Statistical Methods to Handle Missing Data and Account for Statistical Uncertainty Due to Missingness (MD-2):* The primary analyses, which use GEE based on all available observations, assume outcomes are missing completely at random (MCAR). As an initial assessment of missing data patterns, intervention groups (including by relevant subgroups and time point) will be compared with regard to missing outcome rates. We will test for a relationship between missingness and outcomes at early time points to evaluate the plausibility of the MCAR assumption. We will use multiple imputation methods (an established method) to help assure valid inferences. *(d) Plans to Record and Report Dropout and Missing Data (MD-3, IR-7):* The trial data will be managed using REDCap software, currently running at Case Western Reserve University (CWRU). REDCap is a secure web-based application providing an intuitive interface for validated data entry, audit trails for tracking data manipulation and export procedures, and automated export procedures for seamless data downloads to common statistical packages. Missing data reports will be generated weekly from REDCap for timely resolution and reporting purposes. *(e) Plans to Examine Sensitivity of Inferences to Missing Data Methods (MD-4):* As noted above, multiple imputation will be used to obtain valid inferences in the presence of data that are not missing completely at random. We will use predictive mean matching with an appropriate prediction model depending on the outcome (e.g. logistic regression for binary outcomes, linear regression for continuous and count outcomes). Alternative imputation models will be used as part of sensitivity analyses.

Heterogeneity of Treatment Effects (HTE: HT-1, HT-2, HT-3). Our primary hypothesis addresses the effect of interventions at 12 months, as well as the longitudinal effect of the interventions. There is no empiric data on comparative effectiveness of these interventions, but individually they have similar effectiveness from prior literature. In particular, we will assess the possible moderators indicated in Figure 1; specific examples include age (e.g., dichotomized as age < 75 versus age  $\geq$  75), presence of two or more medical conditions, gender, and race. Heterogeneity of treatment effect will be assessed by adding to the GEE models each potential moderator, along with the corresponding interaction with treatment. We will test moderator by treatment interactions to determine evidence for subgroup differences in the treatment effect. Corresponding 95% confidence intervals for the treatment effect for each subgroup will be computed. Secondarily, we will conduct an interaction tree approach such as CHAID (Chi-squared automatic interaction detection) an extension of CART (Classification and Regression Trees) to simultaneously assess the set of potential moderators, and determine subgroups that have significant intervention effects.

**Reporting Plan (IR-5):** To allow for assessment of study's internal and external validity, we will adhere to standard reporting guidelines for randomized clinical trials as specified by: EQUATOR network, SPIRIT 2013 statement; and CONSORT 2010 statement.

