## 5.4 Treatment Assignment Procedures

### 5.4.1 Randomization Procedures (RQ-2)

Randomization is at the level of the cluster (housing facility) for logistical efficiency. This will greatly reduce the potential for error that could otherwise occur with people at the same site assigned to different treatments. Furthermore, keeping the same treatment at each site reduces chances of 'contamination' (i.e. participant discussing their treatment with others). Additionally, stratified cluster randomization will be used, i.e. a block (constrained) randomization approach in which balance over treatments is assured for 2 key cluster-level (stratification) variables, namely facility size (>100 versus ≤100 residents), and geographic location (Cuyahoga County vs other). The project statistician, [name] will generate the randomization scheme for the 22 + 4 additional housing facilities. While the randomization is at the housing level, the study objectives, interventions and primary outcomes all pertain to the individual level (RC-1).

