### 11.2 Sample Size Considerations (RC-3)

For continuous outcomes we computed power using a variance correction (i.e., variance inflation factor) to take into account possible correlations of outcomes within cluster. All computations of required effective samples sizes (or corresponding power) were done using the PASS 2005 software. For binary outcomes, we used a specialized program for cluster randomization (a non-inferiority test comparing two proportions).

The primary outcome tooth pain was defined as change in pain (based on a 100-mm visual analogue pain scale (VAS), where higher is worse pain) from baseline to 1 year. We assume a mean difference of 0 between SDF and ART+FV, and consider non-inferiority to be within a margin (mean difference) of 8 between SDF and ART+FV arms; and based on prior literature also assume a common standard deviation of 25. Further, we assumed an average of 25 subjects recruited per site, an intraclass correlation (ICC) of 0.01 (based on prior studies and literature), and a 15% dropout rate (based on prior studies). The use of a 0.025 alpha-level one-sided t-test to test the null hypothesis of inferiority versus the alternative hypothesis of non-inferiority (as defined above), 11 sites per treatment group (corresponding to 275 subjects per treatment group or 550 total) will provide an estimated 89% power to conclude non-inferiority. Even if the ICC is higher (0.02), there will still be 83% power to detect non-inferiority.

A second primary outcome is arrest rate. Previous data show a high arrest rate (of around 90%) for ART + FV. We expect a similar arrest rate for SDF. For the power calculation we suppose the unit of analysis to be the person, and consider the binary outcome of 'arrest' defined as all lesions for an individual being arrested. We assume equal (person-level) arrest rates of 90% for the ART+FV and SDF groups, and consider non-inferiority to be within a margin (difference in arrest proportions for ART+FV versus SDF) of 0.09. With the same assumptions as before using a 0.025 alpha level one-sided z test, the targeted sample size of 275 subjects in 11 sites per treatment group will provide an estimated 85% power to conclude non-inferiority. For a higher ICC of 0.02, there will still about 80% power to detect non-inferiority.

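### Section 11.4 ties both non-inferiority margins to t and z intervals with no stated allowance for facility clustering, and contradicts itself on whether the GEE is primary

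*Combined protocol and SAP*

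**What the plan says.** Section 5.4.1 sets the unit of randomisation: "Randomization is at the level of the cluster (housing facility) for logistical efficiency". Section 11.2 sizes the trial to match, with 11 sites and 275 participants per arm, an average of 25 per site, 15% dropout, "an intraclass correlation (ICC) of 0.01" and 0.02 as the less favourable case. It inflates the variance for continuous outcomes and uses a cluster-randomisation program for binary ones.

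Section 11.4 holds the only decision rules for the two primary outcomes:

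- Pain: "a 95% confidence interval (CI) based on a t-test for the difference in mean responses" (SDF minus ART+FV) must lie wholly below 8.
- Arrest: "For arrest rate, a 95% CI for the difference in rates (based on a z statistic) will be computed"; it must lie wholly above -0.09.

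Neither rule mentions facility, a design effect, a robust variance or degrees of freedom based on sites. The next paragraph says: "We will seek to corroborate initial results using a generalized estimating equations (GEE) approach". The exchangeable within-site correlation and the small-cluster correction appear only there, and no margin is attached to that model's interval.

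The Missing Data paragraph of Section 11.4 reads differently: "The primary analyses, which use GEE based on all available observations". It does not say which GEE is meant. For the repeated-measures extension, which is labelled secondary, Section 11.4 adds: "If a substantial within-facility correlation is found we may need to incorporate facility as a second cluster levels".

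**The concern.** Outcomes of residents in one facility are expected to be correlated, and Section 11.2 assumes so. An interval that treats participants as independent is then too narrow. In a non-inferiority trial that error favours the claim, and here it would affect both primary outcomes.

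The internal conflict raises a second problem. If the decision rules govern, the inflation above may apply. If the Missing Data paragraph governs and the site-clustered GEE is primary, the inflation does not arise, but no rule links its interval to a margin. For arrest, the link suggested for binary outcomes is the logit. It gives an odds ratio, which cannot be compared directly with a margin of 0.09 on the risk difference. Nothing says what happens if the two analyses disagree, so two analysts following the plan could report opposite conclusions from the same data.

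**Working it through.** **Inputs (Section 11.2).** 275 per arm in 11 sites; 15% dropout; SD 25; pain margin 8; arrest 90% in both arms; arrest margin 0.09; one-sided alpha 0.025; ICC 0.01 or 0.02. Evaluable per arm: 275 × 0.85 = 233.75. Evaluable per site: m = 25 × 0.85 = 21.25.

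**Step 1: reproduce the plan's power.** Design effect DE = 1 + (m − 1) × ICC = 1.2025 (ICC 0.01) or 1.405 (ICC 0.02). Effective n per arm = 233.75/DE = 194.4 or 166.4. Power = Φ(margin/SE − 1.96), with SE = 25√(2/n_eff) for pain and √(2 × 0.9 × 0.1/n_eff) for arrest.

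| | Stated | With DE | Without DE |
|---|---|---|---|
| Pain, ICC 0.01 | 89% | 88.4% | 93.3% |
| Pain, ICC 0.02 | 83% | 83.1% | 93.3% |
| Arrest, ICC 0.01 | 85% | 84.1% | 90.0% |
| Arrest, ICC 0.02 | about 80% | 78.1% | 90.0% |

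The stated power therefore presumes an analysis that accounts for clustering.

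**Step 2: error at the margin if the intervals ignore site.** One-sided error = 1 − Φ(1.96/√DE). For unequal sites, DE = 1 + ((1 + CV²)m − 1) × ICC.

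| Sites | m | DE (ICC 0.01 / 0.02) | Error (ICC 0.01 / 0.02) |
|---|---|---|---|
| 22 equal, 550 enrolled | 21.25 | 1.2025 / 1.405 | 3.7% / 4.9% |
| 26 equal, 590 enrolled | 19.29 | 1.183 / 1.366 | 3.6% / 4.7% |
| 33 equal, 590 enrolled | 15.2 | 1.142 / 1.284 | 3.3% / 4.2% |
| 22, Table 1 sizes (CV 0.685) | 21.25 | 1.302 / 1.604 | 4.3% / 6.1% |
| 33, Table 1 sizes (CV 0.688) | 15.2 | 1.214 / 1.428 | 3.8% / 5.0% |

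The site counts are those given in Sections 4.1 and 5.4.1. The Table 1 rows assume enrolment proportional to tenants. That is an assumption of this review; Section 5 says about 25 per facility. With 22 equal sites, nominal 95% intervals cover 92.6% and 90.2%.

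A simulation (40,000 runs, 11 sites of 21 per arm) gave 3.5% and 4.8% for the unadjusted t rule. It gave 3.9% and 5.1% for the unadjusted z rule at 0.81 versus 0.90. A t test on site means held about 2.4%.

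**Step 3: where the two rules disagree** (22 equal sites, ICC 0.01, t on 20 df = 2.086).

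- Pain, unadjusted: SE = 25√(2/233.75) = 2.313, half-width 1.96 × 2.313 = 4.53. Clustered: SE = 2.313 × √1.2025 = 2.536, half-width 2.086 × 2.536 = 5.29. Observed differences from 8 − 5.29 = 2.71 to 8 − 4.53 = 3.47 pass the first rule and fail the second.
- Arrest: half-widths 0.0544 and 0.0635. Observed differences from −0.09 + 0.0544 = −0.036 to −0.09 + 0.0635 = −0.027 do the same.
- At ICC 0.02 the ranges widen to 2.3 to 3.5 for pain and −0.036 to −0.021 for arrest.

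**The case against.** The strongest reply is that Section 11.2 uses the same test names with clustering built in. It pairs the t-test with a variance inflation factor and the z test with a cluster program, and its power reproduces only on that basis. Section 11.4 may be using the same names for the same cluster-corrected tests. This stands as a possible reading, so the error inflation is conditional. It does not settle the matter, because Section 11.4 does not say so and introduces within-site correlation only with the GEE.

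It can also be said that only the Missing Data paragraph attaches the word primary to a model, and it names the GEE. That model already carries site correlation and a small-cluster correction. True, but the margins still sit with the t and z intervals, and the GEE has no decision rule. The conditional facility term does belong to a model labelled secondary, so it is a minor part of the point.

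On size, the inflation is modest at the planned ICCs and smaller with 33 sites. The disagreement range compares intervals without covariates, whereas the planned GEE is covariate-adjusted, and about 42% of the pain range at ICC 0.01 comes from using 20 df instead of 1.96. With a true difference of zero, ICC 0.01 and 22 sites, the chance of landing in the range is about 6% for pain and 7% for arrest; with 33 equal sites it is about 3% and 4%. Opposite conclusions are possible but uncommon at the planned values. None of this removes the need to say which analysis decides.

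**Conclusion.** The concern holds and should be fixed before analysis. Three facts rest on the text alone: both margins are attached to intervals with no stated clustering allowance, the site-clustered GEE is described as corroborative, and another paragraph of the same section calls GEE primary without giving it a margin.

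The error inflation is conditional on unadjusted intervals. Across the equal-size layouts the one-sided error is 3.3% to 3.7% at ICC 0.01 and 4.2% to 4.9% at ICC 0.02, against 2.5%. The highest figure, 6.1%, needs 22 sites, ICC 0.02 and enrolment proportional to tenants. These results use the plan's SD, arrest rate, dropout and ICCs; a larger true ICC would make them worse.

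**What to change.** In Section 11.4:

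1. Name the site-clustered analysis with small-cluster correction, already described there, as the single primary analysis at 52 weeks.
2. Tie the margins 8 and −0.09 to its 95% interval on the difference scale: identity link for pain; for arrest, a risk difference from an identity link or standardised from the logit model. Base the degrees of freedom on the number of sites.
3. Make any t or z interval that does not adjust for site descriptive.
4. Align the Missing Data paragraph with this, and state that facility clustering is always included, in the repeated-measures model too, whatever correlation is observed.

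The cost is wording and slightly wider intervals. Approximate power by noncentral t on site-based degrees of freedom:

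| Layout | Pain / arrest, ICC 0.01 | Pain / arrest, ICC 0.02 |
|---|---|---|
| 22 equal sites, 20 df | 85.1% / 80.3% | 79.3% / 74.0% |
| 33 equal sites, 590 enrolled, 31 df | 90.1% / 86.1% | 86.5% / 81.9% |
| 33 sites, Table 1 sizes, 31 df | 88.3% / 84.0% | 82.8% / 77.7% |

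Against the stated 89% / 85% and 83% / 80%, the added sites recover the loss if sizes are equal, and most or all of it at Table 1 sizes. Adding randomisation strata or baseline values as covariates could gain precision but is optional.

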## 5 STUDY ENROLLMENT AND WITHDRAWAL

The *original* 22 housing facilities have a total of 3749 tenants 62 years and older, therefore, we will approach 1368 participants, out of whom 958 will be screened for cavities to obtain the target sample of 550 older adults (approx. 25/housing facility) who have at least one natural tooth. Only individuals with severe medical, cognitive or motor impairments will be excluded. Individuals living independently (our study population) will likely not have severe impairments. Severe medical and motor impairments preventing enrollment will be those which would prevent the individual from completing the dental screening. Severe cognitive impairment will be determined through the consent process. If an individual is unable to explain back to the person obtaining consent what the study involves and what they will do, they will not be consented. Recruitment efforts for the main trial will take place over a two-year period. The study staff will approach tenants at various venues and inquire if they are completely edentulous to check study inclusion/exclusion criteria. Following are the estimates based on our prior study: 73% had at least one tooth; 70% providing consent; 58% with untreated caries. We expect a target of 550 participants to be randomized to the two arms.

The recruitment for all housing sites will follow a 2-stage process: (1) all participants consented will participate in the dental screening; (2) participants found to have non-urgent cavities at the screening and who fulfill the inclusion criteria will be enrolled into the clinical trial.

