### 5.1 Subject *Initial* Inclusion Criteria

In the first stage of the enrollment process, an individual must meet all of the following criteria:

- Provide signed and dated informed consent form
- Willing to comply with all study procedures and be available for the duration of the study (1 year)
- Male or female, aged 62 years or older
- Live in a participating older adult housing facility

In the second stage of enrollment process, additional inclusion criteria for continuation and participation in the RCT is based on the dental screening:

- Have at least one untreated root or coronal caries lesion on any permanent tooth with an International Caries Detection and Assessment System (ICDAS) II active lesion score of 3 or greater (localized enamel cavity to extensive cavity).

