**Table 8.1.1 Quantitative Summary of measures, sources, and timeline (IR-4)**

Variable Type	Measure	Scale	Source	Timeline
Intervention by Study Arms	

• Biannual SDF (Arm 1)

• ART + biannual FV(Arm 2)

			$T_0, T_{26}$
Primary Outcome	Clinical dental exam 

• % freq of arrested surface/teeth

• Caries arrest

• overall score

		

• ICDAS Coronal and Root [Dikmen 2015]

	$T_0, T_{26}, T_{52}$

	Self-reported evaluation 
 
• Tooth pain/sensitivity
 
	
 
• overall score
 
	
 
• PROMIS v.1.0 - Pain Intensity 3a [Modified for Dental]
 
• Dental Discomfort Questionnaire [Modified for Adults from Versloot et al. 2006]
 
	T 0 , T 26 , T 52
Secondary Outcomes	Clinical dental exam 
 
• New decay
 
 Self-reported evaluation 
 
• OH-quality of life
 
	
 
• # freq of new decay teeth
 
• GOHRQoL overall score
 
	
 
• ICDAS Coronal and Root [Dikmen 2015]
 
• Geriatric Oral Health Quality of Life (GOHRQoL) [Atchison and Dolan, 1990]
 
	T 0 , T 26 , T 52 T 0 , T 26 , T 52
Process Outcome	
 
• Safety
 
• Satisfaction
 
	
 
• % freq. adverse event
 
• overall score
 
• overall score
 
	
 
• Safety Questionnaire (Pre- and Post-Exam/Treatment [Adapted for Adults from Milgrom et al. 2018]
 
• Treatment Satisfaction Questionnaire for Medication (TSQM) [Modified for Dental]
 
• Satisfaction with New Treatment for cavities [Modified for Adults from Crystal et al. 2017]
 
	T 0 , T 26 , T 52 T 52 T 52

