**Secondary outcomes: Older adults' new decay and GOHRQoL (Arm 1: SDF vs. Arm 2: ART +FV) will be assessed through:**

- Clinical dental exam: A newly carious tooth is defined as any tooth receiving an ICDAS lesion code  $\geq 3$  that received a sound code on the previous dental exam or any tooth surface with an ICDAS filling code  $\geq 3$  that previously did not have one. The number of teeth with new decay or filling will be assessed through clinical dental exams ( $T_0$ ,  $T_{26}$ , and  $T_{52}$ ) and recorded on the ICDAS Assessment form.
- Self-reported evaluation: The Geriatric Oral Health-related Quality of Life (GOHRQoL) consist of 12 questions and will be used to assess the impact of the intervention on participants overall oral health quality of life. The overall score will be calculated with higher scores indicating that the participant has greater oral health Quality of Life. The measures will be collected within two week of the baseline visit, the 26-week visit ( $T_0$ ,  $T_{26}$ ), and 52-week visit exam ( $T_{52}$ ).

**Process outcome: Safety and satisfaction and moderating variables (Arm 1: SDF vs. Arm 2: ART +FV) will be assessed through:**

- The Safety Questionnaire-Revised for Adults consists of 15 main adverse events (i.e., existence of dental insurance, severity of adverse symptoms after receiving the dental treatment) and will be used to identify adverse events. Participants will complete this survey pre- and post-exam/treatment at the baseline visit, 26-week visit, and the 52-week visit, respectively. The treatment satisfaction will be assessed through the treatment satisfaction questionnaire for medication (TSQM) modified for Dental and satisfaction with new treatment for cavities, comprised of six questions. The overall average score will be assessed from these two scales with higher mean score indicating better satisfaction with the study treatment. The measures will be conducted during the baseline visit, follow-up visit, and final exam ( $T_0$ ,  $T_{26}$ , and  $T_{52}$ ).

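### New decay is compared as an unadjusted mean tooth count, and no planned model names the number of sound teeth at baseline, which costs precision and leaves chance dentition imbalance between facilities uncorrected

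*Combined protocol and SAP*

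**What the plan says.** Table 8.1.1 gives the scale of new decay as "freq of new decay teeth". Section 8.1.1 says "The number of teeth with new decay or filling will be assessed through clinical dental exams" and that the result is "recorded on the ICDAS Assessment form", at baseline, 26 and 52 weeks. No denominator is attached.

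The definition in 8.1.1 has two limbs. A tooth counts if it has a lesion code of 3 or more and is one "that received a sound code on the previous dental exam or any tooth surface with an ICDAS filling code" of 3 or more that was not there before. The first limb depends on the tooth having been sound; the second does not.

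Section 5 describes the target sample as people "who have at least one natural tooth". Section 5.1 adds, for entry to the trial, "Have at least one untreated root or coronal caries lesion on any permanent tooth", with an active ICDAS code of 3 or more.

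For outcomes other than pain and arrest, section 11.4 says "For other outcomes, we will also compute 95% CI for differences in means (or proportions for binary outcomes". A GEE with treatment and prognostic variables follows as corroboration. The prognostic variables it names are sociodemographics, medical conditions and oral health behaviours. No section names a tooth count, an offset, a rate per tooth, or a rule for people without a sound tooth.

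**The concern.** Under the lesion limb, only a tooth "that received a sound code on the previous dental exam" can become newly carious. A person with 25 sound teeth has many chances of an event and a person with two has few. That spread exists before treatment and has nothing to do with either strategy. In an unadjusted difference in means it is noise.

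The trial randomises facilities, and section 11.2 plans 11 per arm. With so few clusters, the arms can differ by chance in average dentition, and a difference in teeth would then appear as a difference in prevention. The sound codes must be charted for the definition to work, so the number at risk at baseline is already available and only has to be derived.

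At stake is how well the secondary non-inferiority hypothesis on new decay can be assessed. The primary outcomes are not affected.

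**Working it through.** **The plan's own figures.** There is no power, rate, SD or margin for new decay to reproduce. The cluster assumptions in 11.2 can be checked on tooth pain. After 15% dropout, n = 275 × 0.85 = 233.75 per arm and m = 25 × 0.85 = 21.25 per site. The design effect at ICC 0.01 is 1 + 20.25 × 0.01 = 1.2025, so the effective n is 194.4. With margin 8, SD 25 and one-sided alpha 0.025, power is 88.2% against the stated 89%. The same m is used below.

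**Assumptions, none from the documents.** K is the number of teeth at risk, with mean 12 to 16 and SD 6 to 8, rounded and held to 0–28. The per-tooth 12-month risk r is 0.04 to 0.08. The coefficient of variation (CV) of personal risk is 0 to 1.

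**1. Variance explained by K.** With E(Y|K) = rK and v = (CV × r)²:

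Var(Y) = r²Var(K) + E(K)r(1−r) + E[K(K−1)]v

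The share explained is r²Var(K)/Var(Y).

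- High end (nominal mean 12, SD 8, r = 0.08, CV = 0; after clipping, mean 12.16, SD 7.40): 0.0064 × 54.76 = 0.350; 12.16 × 0.0736 = 0.895; share = 0.350/1.245 = 0.28.
- Low end (nominal mean 16, SD 6, r = 0.04, CV = 1; after clipping, mean 15.95, SD 5.86): 0.0016 × 34.34 = 0.055; 15.95 × 0.0384 = 0.612; E[K(K−1)] = 34.34 + 254.40 − 15.95 = 272.8, × 0.0016 = 0.436; share = 0.055/1.103 = 0.05.

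Simulating 400,000 people in each of the 16 combinations gives the same range, 5% to 28%. The gain in effective participants is 1/(1 − share) − 1: 1/0.95 − 1 = 5% and 1/0.72 − 1 = 39%. This is a person-level figure and ignores clustering.

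**2. Chance imbalance between arms.** SE of the difference in mean K = SD × √[2(1 + 20.25 × ICC)/(11 × 21.25)], with an assumed tooth-count ICC of 0.01 to 0.10.

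| SD | ICC | SE | 1.96 SE |
|---|---|---|---|
| 6 | 0.01 | 0.61 | 1.19 teeth |
| 8 | 0.10 | 1.29 | 2.52 teeth |

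With identical per-tooth risk in both arms, imbalance of this size alone gives a difference of 1.19 × 0.04 = 0.05 to 2.52 × 0.08 = 0.20 new-decay teeth. Relative to the expected count that is 1.19/16 = 7% to 2.52/12 = 21%. More sites, as added later in the protocol, would reduce this somewhat.

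**3. People with no tooth at risk.** If draws outside 0–28 are discarded, about 0.2% to 1.8% have K = 0. If they are set to the nearest limit, about 0.5% to 7.6% do. If such people never score, a difference in means shrinks by that share. With 12 teeth and risks of 5% and 7.5%, the difference is 12 × 0.025 = 0.30 teeth. It becomes 0.30 × 0.998 = 0.299 at 0.2% and 0.30 × 0.92 = 0.276 at 8%.

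**The case against.** **The plan leaves room for this.** The covariate list in 11.4 is open-ended. The sensitivity paragraph allows other predictor sets, other outcome definitions and, for some outcomes, other distributions. That stands, but it permits the adjustment without specifying it.

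**The outcome is exploratory and has no margin.** This also stands. No threshold exists against which dilution could be shown to change a conclusion. Dilution pulls a difference toward zero while a wider interval works against non-inferiority, so the net direction is not established.

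**Randomisation balances tooth number in expectation.** Correct. A confidence interval that reflects clustering already carries the chance imbalance as extra width. Adjustment removes some of that width and corrects for the imbalance that occurs.

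**A reader might infer that people with no sound tooth automatically score zero and are credited as prevention successes.** The documents do not support this. The filling limb in 8.1.1 lets a person with no sound tooth score, and no success is defined for new decay. Such a person adds zero to the mean only if no new filling code appears.

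**A reader might also infer that a rate per tooth at risk should replace the count.** Mean new-decay teeth per person is a legitimate person-level quantity, and section 5.4.1 places the objectives at the individual level. A rate restricted to people with sound teeth asks a different question in a smaller group. It would set a two-limb numerator over a denominator that fits only the lesion limb. The lesion limb also looks back to the previous exam, so at 52 weeks its risk set comes from the 26-week exam.

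**Conclusion.** The point holds as a matter of efficiency and chance imbalance in one secondary outcome. New decay is an unadjusted count, and its most obvious baseline predictor, already derivable from the ICDAS charting, is named in no model. Under the stated assumptions baseline teeth at risk explain about 5% to 28% of the variance, equal to about 5% to 39% more effective participants. Chance dentition imbalance could produce an apparent difference of about 0.05 to 0.20 teeth. The share with no tooth at risk is about 0.2% to 8%, depending on how the distribution is truncated, so dilution is probably small.

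All these sizes rest on assumed tooth counts and decay rates and should be replaced by the trial's own baseline data. The documents do not support a claim of systematic bias toward non-inferiority. The change is desirable and cheap, not essential to the validity of the trial.

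**What to change.** In 11.4, for new decay:

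- Add the number of sound teeth on the baseline ICDAS form as a covariate in the planned site-clustered GEE, fitted as a count model.
- Base the treatment comparison on that adjusted model for all randomised participants, including those with no sound tooth. Keep the raw difference in means as descriptive.
- Report baseline teeth at risk by arm.
- As a sensitivity analysis, fit a model with log(teeth at risk) as offset among people with at least one tooth at risk, giving a rate per tooth at risk. State which exam defines the risk set.

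Before that sensitivity analysis is fixed, clarify in 8.1.1 whether ART restorations placed by the study count under the filling limb. Only Arm 2 receives them, and the documents do not say which code they carry.

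The cost is SAP wording, one derived variable and one extra model. No new data are collected and no one is dropped from the main comparison.
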